6.0 Recruitment Methods

LOCAL:

- 6.4 Interested individuals identified through recruitment strategies will be provided contact information to call the study coordinator for an initial phone screen. The coordinator will use a phone screen script to review details of the study with potential participants. To conduct the initial screen, the coordinator asks participants a series of questions related to study inclusion criteria. If the participant meets the inclusion criteria the coordinator will continue the screen with questions about exclusion criteria. If the individual is eligible and interested, they will then be scheduled for an in-person visit to University of Houston, College of Nursing, to complete their baseline visit and receive their group assignment. At this visit, eligibility will again be confirmed by asking the same series of questions about inclusion and exclusion criteria to confirm their eligibility status. After we confirm eligibility, consent is obtained, and baseline assessments made. We will document reasons for refusal.
- 6.5 Multiple recruitment sites and methods will be used for recruitment. Our primary recruitment site will be MD Anderson Cancer Center (MDACC) facilitated by [name] (study consultant). The distribution of how subjects were contacted and participation rate will be systematically tracked using screening logs. Recruitment feasibility will be assessed by the number of screened and eligible participants and the number of CCGs refusing to participate. Participants may also be sourced from churches, other support groups, social media postings, or by word-of-mouth. Recruitment strategies include presenting the study at monthly staff meetings in various cancer subspecialties, providing study brochures to oncologists, nurses, and administrative staff to be passed on to patients and their families, presenting at CG support group events, and posting the study on relevant hospital web sites including those specific to recruiting volunteers into clinical trials. In addition, participants will be recruited through non-hospital online websites such as the Houston Chapter of the Oncology Nursing Society and the Family Caregiver Support Network. Other strategies include targeted advertising in local newspapers and posting of flyers in public places (e.g., library, senior centers).
- 6.6 Potential subjects may be identified by their attendance at support groups for cancer caregivers. They may also be identified at any of the functions listed above if they mention to a member of the research team that they are currently a caregiver for a cancer patient. Study consultants will also work to identify potential participants and provide them with information about the study if they are interested. Potential

FULL PROTOCOL TITLE: CARING FOR CAREGIVERS WITH MIND-BODY EXERCISE

subjects may also be identified if they contact a member of the research team after encountering the study flyer or speaking with a past study participant.

- 6.7 The materials used for recruitment include a study flier and PowerPoint presentations (when information about the study is presented to a group).

7.0 Study Timelines

7.1 For Cohorts 1 and 2, we will randomize (1:1:1) 24 CCGs to one of three conditions: (1) A community- based Qigong program; (2) an internet-based Qigong program; or (3) a self-care control group. For Cohort 3, we will randomize (2:1) 15 CCGs to one of two conditions: (1) an internet-based Qigong Program, or (2) a self-care control group. For Cohort 4, we will randomize (2:1) 15 CCGs to one of two conditions: (1) a community-based Qigong program, or (2) a self-care control group. Our primary outcomes are feasibility and acceptability.

7.2 Participants in the community-based programs will attend one, 75 minutes class per week supplemented by home practice (guided by printed materials) for 20 minutes on 3 additional days. Participants in the internet-guided program will be asked to follow two online sessions for 40 minutes each, also supplemented by home practice for 20 minutes on 3 additional days. Participants in both Qigong groups will commence training within 2 weeks of baseline visits. Caregivers randomized to either Qigong intervention can expect a total time commitment of 30 hours to complete all study related activities.

Individuals randomized to the self-care control group will be provided with an educational book on caregiving, they will also be provided with a “Self-Care Manual” that includes self-guided activities related to caregiving and caregiver health. Caregivers randomized to this group can expect about a 5-hour total time commitment to study related activities.

7.3 Baseline and 12-week assessments including psychosocial measures and QOL, physical function and cognitive measures will occur in person for all participants at the University of Houston College of Nursing in Sugarland, [name]. In addition, a short qualitative interview will be conducted with participants in the community-based and internet-based classes. A longer-term 6-month follow-up will assess psychosocial and QOL measures using a mail-in questionnaire packet. Primary analyses should be complete by 08/31/2021.

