5.0 Number of Subjects

LOCAL:

5.1 We expect to consent, enroll, and randomize a total of 54 CCGs.

5.2 The sample size was based on practical/budgetary constraints as well as a preliminary power analysis. A power analysis was conducted to determine the minimum sample

FULL PROTOCOL TITLE: CARING FOR CAREGIVERS WITH MIND-BODY EXERCISE

size that is required to find significance with a power set of .80, an alpha level at .05, correlation among the repeated measures of 0.3, and a moderate effect size of .25 using G*Power version 3.1. Based on the primary analysis, to ensure sufficient power on the repeated measure ANOVA (3 time points x 3 groups), a total of 48 participants are required. In consideration of 10-15% of attrition rate, a total of 54 participants will be recruited.

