18.0 Process to Document Consent in Writing

18.1 This study will be following “SOP: Written Documentation of Consent (HRP-091).”

19.0 Data Management

19.1 Data will be managed using the REDCap data management system supported through UH. REDCap is a secure, web-based application for managing online databases. REDCap provides automated export procedures for seamless data downloads to Excel and common statistical packages such as SAS. Case report forms will be produced using built-in features of REDCap.

Feasibility. We will use descriptive statistics to evaluate recruitment and retention rates, attendance at classes, and adherence with online intervention. Retention rate will be reported by group at the end of the study. Attendance will be recorded as the proportion of classes attended for community-based classes; and online video tutorial use, logs of home practice, numbers of logins to the webpage, clicks on education links, downloads and views of videos for the internet-based classes. We will consider study retention successful if the retention rate is at least 80% at 12 weeks, and attendance at in-person classes and home compliance to internet-based lessons is at least 70%. Similar criteria will be set for internet-based compliance as well as home practice compliance in both groups. We will test for non-inferiority of the observed rates relative to the expected rates of retention and attendance assuming that the retention and attendance rates follow a beta-binomial distribution. Non-inferiority margins will be determined as 90% lower confidence bounds on the estimated rate for participants in each group. Maximum likelihood will be used to obtain significance and confidence intervals. Relative risk of non-completion between each Qigong training method and self-care control group will be used to represent study completion rates with inference based on separate Fisher’s exact tests.

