Estimating variance for future power calculations. We will use linear mixed models with fixed effects of visit and treatment x post-baseline visit interaction and unstructured covariance among repeated measures to analyze efficacy outcomes. This will yield six variance components required for future power calculations. The Wald statistic from the treatment x visit interaction testing 12-week treatment-dependent response will be used to estimate the effect of Qigong and as a criterion for selecting outcomes that are potentially sensitive to Qigong. Selection of the outcomes to include in our future trial, and which to select as the primary outcome, will also be

FULL PROTOCOL TITLE: CARING FOR CAREGIVERS WITH MIND-BODY EXERCISE

guided by consideration of clinical relevance, participant burden, and cost. The study will have 80% power to identify the outcome that is truly most responsive to Qigong from among the 14 measures calculated from the 12 assessments completed at 12 weeks if the most responsive measure is associated with an effect size at least 0.43 SD greater than the others.

Inter-rater reliability and validity testing of proficiency instrument. Inter-rater reliability will be evaluated using Cohen's Kappa statistic. Validity testing based on cross-sectional comparisons of proficiency scores and practitioner's years of training will utilize Pearson's correlations. Associations between longitudinal changes in proficiency and clinical outcomes will be evaluated using mixed model approaches described above.

Qualitative analysis. Semi-structured qualitative interviews will be audio recorded and transcribed verbatim. Thematic analysis will be informed by grounded theory methods to guide description of qualitative interviews. Questions will focus on facilitators/barriers to recruitment/participation, and acceptability of the intervention and its specific components. Two investigators will independently code transcripts to identify emergent themes in an iterative process until thematic saturation is reached as in prior studies.^{47, 48 49-51} Transcription, coding, and analysis will be conducted in NVivo v11.

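### The arms on offer differ by cohort, but neither the mixed model nor the completion relative risks adjust for cohort, so each Qigong-versus-control contrast is partly confounded with cohort

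*Combined protocol and SAP*

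**What the plan says.** Section 7.1 sets out three randomisation schemes. "For Cohorts 1 and 2, we will randomize (1:1:1) 24 CCGs to one of three conditions": community Qigong, internet Qigong or self-care control. Then "For Cohort 3, we will randomize (2:1) 15 CCGs to one of two conditions: (1) an internet-based Qigong Program", the alternative being self-care control. Finally "For Cohort 4, we will randomize (2:1) 15 CCGs to one of two conditions: (1) a community-based Qigong program", again against self-care control. Section 5.1 gives the total: "We expect to consent, enroll, and randomize a total of 54 CCGs".

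Section 19.1 describes the analysis. Efficacy outcomes go into "linear mixed models with fixed effects of visit and treatment x post-baseline visit interaction", with unstructured covariance. On its use, the plan says: "The Wald statistic from the treatment x visit interaction testing 12-week treatment-dependent response will be used to estimate the effect of Qigong". The same statistic is a criterion for choosing outcomes for the later trial. For completion, the plan reports "Relative risk of non-completion between each Qigong training method and self-care control group", with a separate Fisher's exact test for each.

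Cohorts are mentioned only in section 7.1. No analysis text gives a cohort term, a stratified comparison or a rule limiting controls to those randomised concurrently. Section 7.1 also says "Our primary outcomes are feasibility and acceptability".

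**The concern.** Randomisation protects a comparison only among people who could have been assigned to either arm. No one in Cohort 3 could receive community Qigong, and no one in Cohort 4 could receive internet Qigong. Pooling all controls across cohorts mixes a randomised comparison with a comparison between cohorts.

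The mixed model has no treatment main effect, so it assumes equal baseline means across arms. That is a sound device under simple randomisation, but here randomisation supports it only within a cohort.

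The documents do not show that Cohorts 3 and 4 will differ, but they give reasons why they might. Section 12.2 expects caregivers with flexible schedules to favour classes and those who cannot leave home to favour self-guided training. Section 10.1 fixes the classes at one weekday afternoon slot. Section 1.2 plans enrolment over a year, and section 6.5 lists many recruitment sources. That different people would agree to an internet-or-control cohort and a community-or-control cohort is an inference, though a reasonable one.

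At stake is the relative standing of the two delivery modes. A cohort difference enters their estimates with opposite signs, so one looks better and the other worse. These estimates inform the larger trial, which section 12.2 says will study both modes.

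**Working it through.** **Inputs.** Cohort sizes and ratios are from section 7.1, the total of 54 and the correlation of 0.3 from section 5, and the model terms and completion contrast from section 19.1. The counts below assume the ratios are met exactly.

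**The plan's own figures.** 24 + 15 + 15 = 54, which matches section 5.1 (24 must be the combined size of Cohorts 1 and 2; 24 in each would give 78). The 48 in section 5.2 also reproduces: a group-by-time interaction test with 3 groups, 3 times, f = 0.25, correlation 0.3 and alpha 0.05 has power 0.810 at N = 48, and 48/0.90 rounds up to 54. That calculation has no cohort input.

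**Allocation.**

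| Stratum | Community | Internet | Control |
|---|---|---|---|
| Cohorts 1–2 | 8 | 8 | 8 |
| Cohort 3 | 0 | 10 | 5 |
| Cohort 4 | 10 | 0 | 5 |
| Total | 18 | 18 | 18 |

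**Bias.** Let D be the Cohort 4 minus Cohort 3 difference that is unrelated to treatment. The bias is D times the difference between arms in the share from Cohort 4; the Cohort 3 shares differ by the same amount in the opposite direction.

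- Community v control: 10/18 − 5/18 = 5/18, so +0.278D.
- Internet v control: 0/18 − 5/18 = −5/18, so −0.278D.
- Pooled Qigong v control: 10/36 − 5/18 = 0, because every stratum is 2:1 Qigong to control.

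For D of 0.25, 0.5 and 1.0 SD (assumed) at follow-up only, the bias is 0.07, 0.14 and 0.28 SD. If the same shift is present at baseline, the model removes part of it and about 0.05, 0.10 and 0.17 SD remains.

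**Type I error.** Simulation used 40,000 trials per cell, a baseline-adjusted 12-week contrast and correlation 0.3. The shift was either split between Cohorts 3 and 4 or placed in Cohort 4 only; ranges cover both.

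| Test, no cohort term | D = 0 | 0.25 | 0.5 | 1.0 |
|---|---|---|---|---|
| Arm v control, t | 4.9–5.0% | 5.3–5.5% | 6.5–6.7% | 10.5–11.7% |
| Arm v control, large-sample Wald | 5.4–5.8% | 5.8–6.0% | 7.2–7.4% | 11.2–12.8% |
| Three-arm 2-df, F | 4.9–5.0% | 6.2–6.4% | 9.8–10.2% | 23.6–26.4% |
| Three-arm 2-df, chi-square | 5.8–5.9% | 7.2–7.4% | 11.4–11.5% | 26.0–29.2% |

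With the shift at both visits, arm v control gives 5.0–5.3%, 5.4–5.9% and 7.2–7.9% (t), or 5.5–5.8%, 6.3–6.5% and 7.7–8.6% (large-sample Wald). With stratum in the model, t and F tests stay at 4.7–5.2% throughout.

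**Completion.** Assume no arm effect and non-completion of 20% in Cohorts 1–2, 10% in Cohort 3 and 30% in Cohort 4.

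- Community: (8×0.2 + 10×0.3)/18 = 0.256.
- Internet: (8×0.2 + 10×0.1)/18 = 0.144.
- Control: (8×0.2 + 5×0.1 + 5×0.3)/18 = 0.200.

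The unstratified relative risks are 1.28 and 0.72; the Mantel-Haenszel relative risks are 1.00. With a milder 15% and 25% in Cohorts 3 and 4, the unstratified values are 1.14 and 0.86. In the 20/10/30% case the Fisher tests reject about 2.9% of the time, so they are not inflated above 5%; the distortion is in the estimates.

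**Precision after adjustment** (variances in units of σ²).

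- Each arm v control, unadjusted: 1/18 + 1/18 = 0.1111, SE 0.333.
- With stratum fixed effects: 0.1275, SE 0.357 (+7%).
- Within strata where the arm was open only (13 controls): 1/(8×8/16 + 10×5/15) = 1/7.33 = 0.136, SE 0.369 (+11%).
- Pooled Qigong v control: 1/36 + 1/18 = 0.0833, SE 0.289 with or without stratum.
- Community v internet: SE 0.333 to 0.420 (+26%).

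**The case against.** Section 19.1 speaks of the effect of Qigong in the singular and may intend one pooled contrast. On that reading the model estimate is unbiased at the planned counts, and only the completion relative risks, which are explicitly by arm, are affected. This is fair as far as it goes. But the plan names three treatment conditions and does not say whether the interaction test is pooled, by arm or on 2 df, so the pooled reading cannot be assumed.

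D is entirely assumed and could be zero; eligibility criteria and assessment site are common to all cohorts. If cohorts differ in lasting case mix, the smaller both-visit figures apply, and at 0.25 SD the t-based error rate is close to nominal. The upper ends of the Wald and chi-square ranges also include small-sample inflation that is present at D = 0. All of this stands, and it limits the size of the problem.

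The completion estimates are noisy in any case. With about 3.6 events per arm, the SE of the log relative risk is √(2×(1/3.6 − 1/18)) = 0.67, so a shift to 1.28 is about 0.37 SE. This stands too, but noise does not justify a systematic error that analysis by stratum removes.

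Stratifying has its own cost. In the 20/10/30% case, the chance of no control events is 0.8⁸×0.9⁵ = 9.9% for the stratified internet comparison, against 1.7% unstratified; for community it is 2.8%. This is a reason for care in choosing the stratified method, not for leaving cohort out. Finally, the model's 0.357 SE borrows indirect information by assuming that treatment effects are the same in every stratum; 0.369 is the figure without that borrowing.

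**Conclusion.** The concern holds. As written, the arm-versus-control estimates are not fully protected by the randomisation, and a difference between Cohorts 3 and 4 biases them by 5/18 of its size in opposite directions. Confounding is partial: Cohorts 1 and 2 contribute equally to all arms, and each Qigong arm has controls in every cohort that offered it, so the effects remain estimable once stratum is in the analysis.

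The practical size depends on an unknown D. It is negligible at 0.25 SD, modest at 0.5 SD and material at 1.0 SD, especially if the outcome-selection statistic is a 2-df test. Checks against fixed feasibility targets, kappa, the validity correlations and the qualitative work are not arm contrasts and are unaffected. Since the primary outcomes are feasibility and acceptability, this concerns secondary estimates. It should be fixed because the remedy is cheap, but it does not threaten the pilot's main purpose.

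**What to change.** Amend section 19.1 as follows.

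1. Add randomisation stratum (Cohorts 1–2, Cohort 3, Cohort 4) and stratum-by-visit as fixed effects in the mixed model. State whether the treatment-by-visit Wald statistic is pooled, by arm or on 2 df.
2. Replace the unstratified relative risks of non-completion for each Qigong arm v control with cohort-stratified ones (Mantel-Haenszel or exact). An exact stratified method copes better with strata that have no control events. Show the counts by stratum and arm.
3. State that community and internet Qigong are directly randomised against each other only in Cohorts 1 and 2, 8 v 8.

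The change is to wording only; the sample size is unaltered. Three strata add 2 + 2×2 = 6 fixed-effect parameters for outcomes with three visits, and 2 + 2 = 4 for those measured only at baseline and 12 weeks, with 54 participants. The loss of precision is as calculated above: 7% in SE for each arm v control and none for pooled Qigong v control. The 26% rise for community v internet reflects how little direct randomised information there is on that comparison.

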8.0 Study Endpoints

8.1 This is a minimal risk study. There are no safety endpoints given there are no safety risks associated with the study.

9.1 Procedures Involved

9.1 Using CCGs as a representative population of the larger CG population, our long-term goal is to conduct a large-scale fully powered trial evaluating a widely accessible and previously studied Qigong regimen (Eight Brocades, Baduanjin

FULL PROTOCOL TITLE: CARING FOR CAREGIVERS WITH MIND-BODY EXERCISE

Qigong). Interventions will be delivered either in community-based groups led by instructors or via internet to individuals learning thru recorded guided instruction

FULL PROTOCOL TITLE: CARING FOR CAREGIVERS WITH MIND-BODY EXERCISE

supplemented with intermittent virtual live feedback from instructors. Outcomes will include QOL, fatigue, sleep disturbances, psychological distress, CG burden, and physical function. The short-term goals of this R34 are to conduct a mixed-methods pilot randomized controlled trial (RCT) to inform the feasibility and design of a definitive trial. We will address these goals by randomizing 54 CCGs to one of three conditions: (1) A community-based Qigong program; (2) an internet-based Qigong program; or (3) a self-care control group.

9.2 At the baseline visit, eligibility will be confirmed, consent will be obtained, and the consent process will be documented. Written informed consent will be obtained by the research assistant or study staff. The subject will be asked to review the study consent form. Investigator or research staff will meet with the subject to review the form, to confirm the subject's understanding of the study, and to answer any questions that the subject might have. Once the subject demonstrates understanding of the study and agrees to participate in the study, the consent will be signed in the presence of the investigator or research staff. Informed consent will be obtained and reviewed by the University of Houston Institutional Review Board as appropriate. For the duration of the Covid-19 Pandemic, all participants and research staff will follow the University of Houston Department of Research's Covid-19 precautions. These precautions will be followed during any in-person assessment or in-person Qigong class. All participants and research staff will have a contactless temperature screening prior to any in-person activity. Masks will be worn and social distancing maintained during all in-person assessments and in-person Qigong classes.

At the initial visit at University of Houston, College of Nursing, participants will complete informed consent. This date will be recorded on a case report form as the date of enrollment into the study.

In addition, at this visit initial assessment related to QOL, psychological well-being, caregiver burden, cognitive and physical function will be measured. All outcomes will be assessed at baseline and 12 weeks, following completion of the 12-week intervention. All in-person assessments will be conducted by trained research assistants. Baseline and follow-up assessments are estimated to require 2.0 hours.

At the baseline and 12-week appointments, consented participants will be videotaped performing the Eight Brocades. This video will help assess learnability of the intervention and help with the development of the scoring instrument.

Semi-structured, open-ended interviews lasting approximately 30 minutes will be conducted at the 12-week assessment for participants in all groups. Questions will focus on characterizing participants' perceived effectiveness and enjoyability of the Qigong intervention, both community-based and internet-based, and identifying facilitators and barriers to participation. Questions specific to the mode of intervention delivery may include those related to use of technology, the role of face-to-face instructor feedback, perceived motivators to adherence, and self-efficacy.

In weeks 1, 2, 4 and 6 of the program, participants will participate in a one-to-one call with a Qigong instructor. This call will be audio recorded and will give participants

FULL PROTOCOL TITLE: CARING FOR CAREGIVERS WITH MIND-BODY EXERCISE

the opportunity to address any training- related questions or concerns, and to receive personalized feedback and encouragement from the instructor. At the 12-week assessment, participants will be asked to return the computer tablet. Participants will

FULL PROTOCOL TITLE: CARING FOR CAREGIVERS WITH MIND-BODY EXERCISE

be asked to keep track of their home Qigong practice on provided logs throughout the study. We will ask participants to send their logs to the study researchers at the end of each week, and we will provide them with stamped envelopes for mailing.

9.3 The Qigong Instrument used is the Eight Brocade Protocol. Qigong is an increasingly popular multi-modal mind-body exercise that shows promise in addressing a broad range of psychosocial and physical factors highly relevant to CGs. Sharing many characteristics with Tai Chi, Qigong incorporates elements of slow gentle movement, breath training, and a number of cognitive skills including heightened body awareness, focused mental attention, and imagery—which collectively may afford greater benefits to health compared to unimodal therapies.²⁸⁻³⁰

Week	Activities	Approx. Duration (in minutes)
1-2	Check-in	2
	Qigong Warm-up Exercises	
	Qigong Swinging and Drumming the Body	
	Swinging Up and Down	
	Spiraling the Waist	
	Mindful stretching	
	Lower Extremities (feet, ankles, knees)	20
	Upper Extremities (hands, arms, shoulders)	
	Spinal Cord Breathing	
	Washing with Qi from the Heaven	
Tan Tien Breathing		
Introduction to Eight Brocades Movements #1-4	35	
#1 Holding the Hands High to Regulate Internal Organs		
#2 Posing as an Archer Shooting Both Left- and Right-Handed		
#3 Holding One Arm Aloft to Regulate Spleen and Stomach		
#4 Looking Backwards to Prevent Sickness and Strain		
Cool-Down Exercises	3	
Self-massage and meridian tapping		
3-8	Check-in	2
	Qigong Warm-up Exercises	10
	Review/ Practice Eight Brocades Movements #1-4	15
	Learn and practice Eight Brocades Movements #5-8	30
	#1 Swinging the Head and Lowering the Body to Relieve Stress	
	#2 Moving Hands Down Back and Legs, and Touching Feet to Strengthen Kidneys	
	#3 Thrusting Fists and Making Eyes Glare to Enhance Strength	
	#4 Raising and Lowering the Heels to Cure Diseases	
Cool-Down Exercises	3	
9-12	Check-in	2
	Qigong Warm-up Exercises	10
	Review/ Practice/ Refine Eight Brocades Movements #1-8	45
	Cool-Down Exercises	3

9.4 In addition to caregiver distress, medical history and demographics, the following outcomes will be assessed at baseline, 12-weeks, and 6-months:

The following will be measured at baseline and 12-weeks:

FULL PROTOCOL TITLE: CARING FOR CAREGIVERS WITH MIND-BODY EXERCISE

- Grip strength of the dominant hand will be measured using a **Jamar hydraulic hand dynamometer** (Patterson Medical – Canada, Mississauga, ON, CAN).⁴⁴
- **Timed Up-and-Go Single and Dual Task** will be completed among participants. For the single task, CGs will be asked to sit in a chair with their back against the back of the chair. When the researcher says, “Go,” the participant will walk briskly around a marker on the floor and back to the chair. The stopwatch is stopped when the participant’s backside and back are against the chair. For the dual task, the participant completes the steps above in addition to counting backwards by 3s from 100. Both tests will involve two trials.
- **Digit Span**⁴⁵ measures verbal short-term memory. Participants will be asked to repeat numbers in a specific order. Performance is indicated by the average number of digits correctly remembered.
- **Trail Making Test** Parts A & B⁴⁶ consist of 25 circles distributed over a sheet of paper. Participants are timed as they connect the circles without lifting the pen or pencil from the paper.

The following is a table of study measures:

Measure	Description
QOL	
 • Promis-29. 29 items consisting of self-reported health measures in the domains of physical health, mental health and social health.
Depression	
 • Patient Health Questionnaire-9 (PHQ-9). 9 items measuring depression and used to grade severity of symptoms.
Anxiety	
 • Generalized Anxiety Disorder (GAD-7). 7 item tool used for screening, diagnosis and severity assessment of anxiety disorder.
Fatigue	
 • Brief Fatigue Inventory (BFI): 9 items measuring the severity of fatigue and the impact of fatigue on daily functioning in the past 24 hours.
Perceived Social Support	
 • Multidimensional Scale of Perceived Social Support (MSPSS). 12 item scale designed to measure perceived social support from three sources; Family, Friends and a Significant Other.
Sleep Disturbances	
 • Pittsburgh Sleep Quality Index (PSQI): 19 items measuring patients’ sleep quality, sleep latency, sleep duration, habitual sleep efficiency, sleep disturbances, sleeping medication use, and daytime dysfunction over the past month.
Perceived Stress	
 • Perceived Stress Scale (PSS). 10 item psychological instrument measuring the perception of stress.
Caregiver Burden	
 • Caregiver Burden Scale (CBS): 14 items measuring the impact of caregiving on three dimensions of burden: objective, subjective demand, and subjective stress.

FULL PROTOCOL TITLE: CARING FOR CAREGIVERS WITH MIND-BODY EXERCISE

Exercise self-efficacy	
• Self-Efficacy Scale: 13 items measuring self-efficacy expectations related to the ability to continue exercising in the face of barriers to exercise.
Physical Activity	
• Godin Leisure-Time Exercise Questionnaire: 4 items measuring the frequency of light-intensity, moderate-intensity, and vigorous-intensity leisure-time physical activity.

